3.0 Study Endpoints

Below is a table of the study endpoints and outcomes.

Type	Name	Time Frame	Brief Description
Primary	7-day point prevalence tobacco abstinence at the end of treatment (Week 12)	Final 7 days of treatment (Week 12)	7-day point prevalence abstinence from tobacco at the end of treatment (Week 12) will be assessed via biochemical verification and participant self-report and rates of abstinence will be compared between cannabis co-users and tobacco only controls.
Secondary	Changes in cannabis use during tobacco cessation treatment (among co-users)	Final 4 weeks of study treatment (Weeks 8-12)	Among cannabis co-users, cannabis use rates and amounts during the final 4 weeks of tobacco treatment (Weeks 8-12) will be assessed and

			nicotine dependence will be the primary model predictor.
Other: Exploratory	Cannabis co-use severity on tobacco cessation (among co-users)	Throughout trial participation	Tobacco abstinence and indicators of tobacco reduction (average cigarettes per day, quantitative cotinine, etc.) throughout the trial will be examined as a function of baseline cannabis use severity (determined by days of use in the past 30) to assess for dose-dependent impact on tobacco outcomes based on cannabis use severity.

4.0 Inclusion and Exclusion Criteria/ Study Population

Adult tobacco users (ages 18-40) who are motivated to quit smoking (N=208) will be recruited for the study.

Inclusion criteria:

- a) Between the ages of 18 and 40 years old
- b) Must be able to understand the study and provide written informed consent
- c) Daily cigarette smoker for \geq 6 months, smoking \geq 5 cigarettes per day
- d) Must submit a breath carbon monoxide (CO) sample of \geq 7 parts per million (ppm) and/or a positive qualitative cotinine test at the screening visit
- e) Be interested in quitting smoking tobacco cigarettes (defined as a 5 or above on a 10-point Likert scale assessing interest in quitting [1=not at all interested, 10=extremely interested])
- f) Must be willing to take varenicline for the standard 12-week course of treatment
- g) If female, agreement to use birth control (any form) to avoid pregnancy during study procedures

Additional inclusion criteria will be implemented for cannabis co-users, which include:

- h) Self-reported use of cannabis on at least 10 out of the past 30 days or submit a positive qualitative urinary cannabinoid test at screening (limit of detection is 50 ng/ml)

Exclusion criteria:

- a) Any serious or unstable medical/psychiatric disorder (including severe substance use disorders, other than cannabis or tobacco use disorders) or other significant concern in the past three months that may interfere with study performance, impact participant safety, compliance with study procedures, or potentially confound the interpretation of findings
- b) Currently pregnant, lactating, or contemplating pregnancy in the next 6 months
- c) Current use of medications with smoking cessation efficacy
- d) Use of any medications that would interfere with varenicline (i.e., tafenoquine or quinolones)
- e) Regular use of other tobacco or nicotine products other than combustible cigarettes (e.g., smokeless tobacco, electronic cigarettes, etc.) in the past month prior to the quit attempt

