Biochemical Verification of Tobacco, Cannabis, and Other Substances: At each study visit, a urine sample will be collected and an instant-read urine drug screen will be conducted, which includes a qualitative urinary cannabinoid test (cut-off of 50 ng/ml) to determine cannabis use status, as well as assays for other commonly used substances (amphetamines, opioids, etc.). Urinary cotinine (a metabolite of nicotine) will be the primary indicator of tobacco abstinence (83). Qualitative urinary cotinine will be tested via instant-read, immunoassay test strips for purposes of contingency management. Urine samples will be aliquoted and delivered to the laboratory for determination of quantitative cotinine levels. Abstinence criteria for quantitative cotinine will be set at 80 ng/ml. Urinary quantitative cannabinoid values (11-nor-9-carboxy- Δ 9-tetrahydrocannabinol; THCCOOH) will be tested at MUSC. Urine creatinine will also be obtained, to allow for creatinine-normalized urine cannabinoid levels. Saliva samples will be collected for 10 study participants at one time point. A saliva sample may be collected in addition to other biochemical measures for quality improvement purposes and will not be used for research purposes.

Substance Use Assessments: Several substance use assessments will be conducted throughout the study, including; detailed use history (for all substances), dependence level, motivation to quit (tobacco and cannabis), craving, withdrawal, satisfaction and subjective effects (cannabis and tobacco), and motives for use (full listing in Table 2). TLFB procedures (84) will be used at screening (30-day calendar) to assess the frequency and quantity of tobacco use (cigarettes per day and other tobacco use), cannabis, alcohol and other drug use. In order to determine an individual-specific cannabis unit, cannabis quantification procedures will be conducted at screening and as needed when new methods of cannabis use are endorsed. For plant material-based methods, grams of cannabis will be estimated using a surrogate substance (78).

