Prior/Concomitant Medications	X	X	X	X	X	X	X	X	X	X	X	X	X	X	X	X
MINI International Neuropsychiatric Interview	X															
Columbia Suicide Severity Rating Scale (C-SSRS) – Clinician Administered	X ^a															
Hospital Anxiety and Depression Scale (HADS)	X	X	X	X	X	X	X	X	X	X	X	X	X	X	X	X
Urine Pregnancy Test (females only) ^a	X		X			X			X			X			X	
Biochemical Measures of Substance Use																
Carbon Monoxide	X	X	X	X	X	X	X	X	X	X	X	X	X	X	X	X
Urine Drug Screen (instant-read) ^g	X	X	X	X	X	X	X	X	X	X	X	X	X	X	X	X
Urine Cotinine (lab assay and instant-read) ^g	X	X	X	X	X	X	X	X	X	X	X	X	X	X	X	X
Urine Cannabinoids (lab assay)* ^g	X	X	X	X	X	X	X	X	X	X	X	X	X	X	X	X
Substance Use Assessments																
Substance Use History	X															
Timeline Follow-Back	X	X	X ^b	X ^b	X ^b	X ^b	X ^b	X ^b	X ^b	X ^b	X ^b	X ^b	X ^b	X ^b	X ^b	X
Tobacco																
Fagerström Test for Nicotine Dependence (FTND)	X						X ^f			X ^f					X	X
Stages of Change - Short Form (Tobacco)	X															
Readiness/Confidence/Interest to Quit Smoking	X	X	X													
Minnesota Nicotine Withdrawal Scale	X		X	X	X	X	X	X	X	X	X	X	X	X	X	X
Modified Cigarette Evaluation Questionnaire	X		X	X	X	X	X	X	X	X	X	X	X	X	X	X
Questionnaire on Smoking Urges – Brief	X		X	X	X	X	X	X	X	X	X	X	X	X	X	X
Smoking Abstinence Self-Efficacy	X						X ^f			X ^f					X	X
Wisconsin Predicting Patient's Relapse	X															
Quit Smoking Methods															X	X
Cannabis																
Cannabis Quantification	X ^c															
Cannabis Use Disorder Identification Test-Revised	X															X
Cannabis Quit Interest	X ^d		X				X ^f			X ^f					X	X
Marijuana Craving Questionnaire	X		X	X	X	X	X	X	X	X	X	X	X	X	X	X
Modified Lyons Battery for Subjective Effects	X		X				X ^f			X ^f					X	X
Marijuana Problems Scale	X		X				X ^f			X ^f					X	X
Cannabis Withdrawal Scale	X		X				X ^f			X ^f					X	X
Marijuana Motives Measure	X															
Patterns of Co-Use Assessment	X		X				X ^f			X ^f					X	X
Acceptability Surveys																
Medication Acceptability Survey															X	
Participant Satisfaction Survey																X
Co-Use Treatment Preferences Survey																X
Medication Safety/Adherence																
Vital Signs ^a																
Blood Pressure, Pulse	X			X												
Height [screening]																
Weight [screening, Weeks 12 and 26]																
Adverse Events	X	X	X	X	X	X	X	X	X	X	X	X	X	X	X	X
Medication Adherence																
Pill counts				X	X	X	X	X	X	X	X	X	X	X	X	X

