Participant Compensation: Participants will be compensated \$40 for the Screening visit and \$30 per visit for Training, Day 0, other weekly visits (13 visits) and/or early termination (ET) that occurs at any point other than during the Week 12 window (\$50 for Week 12 window visits). They will be compensated \$50 for the end-of-treatment visit (Week 12), and \$50 for the 6-month follow-up visit (Week 26). Compensation is based on completion of all study procedures. Partial compensation may be given for partially completed study visits. For example, payment amounts for remote visits will be contingent on return of the urine sample to study staff at the next in-person study visit. Compensation will be delivered contingent on tobacco abstinence at weekly visits starting at Week 2 (\$20 per visit; \$220 possible). Participants will be compensated for completing daily dairies and medication videos during the 12-week treatment phase. Compensation amount for remote surveys and videos will be based on the percentage of videos and morning reports completed over the past week and will be paid at weekly visits. The compensation scheduled based on the percentage of completed sessions is shown to the right (\$300 maximum for $\geq 90\%$ compliance over 12 weeks). Participants may earn a total of \$1,050 for study participation and completion of all study procedures.

Medication Videos and Logs (% completed each week)	Payment
90-100% compliance	\$25
80-89.9% compliance	\$20
70-79.9% compliance	\$15
50-69.9% compliance	\$10
30-49.9% compliance	\$5
<30% compliance	\$0

Payment for study visits will be made using a pre-paid debit card, called a ClinCard. It works like a bank debit card and participants may use the card to purchase goods or services everywhere Debit MasterCard is accepted. Participants will be given or mailed a ClinCard at the beginning of the study. Each time they receive payment for participation in this study, the money will be added to the card, as outlined in the payment schedule above. Details of the debit card system are explained on an additional sheet.

If an Unscheduled Visit is required during study participation, the participant will be compensated \$10/visit in return for the time and travel demands asked of them.

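### Breath CO alone can satisfy the biochemical entry test, but abstinence is verified by urinary cotinine, so a participant can enrol already below the abstinence cut-off

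*Combined protocol and SAP*

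**What the plan says.** **Entry (section 4.0).** Criterion c covers smoking history: "Daily cigarette smoker for" at least 6 months, at 5 or more cigarettes per day. Criterion d is the biochemical check: breath CO of at least 7 "parts per million (ppm) and/or a positive qualitative cotinine test at the screening visit". Either marker is enough. Co-users must also meet criterion h: "Self-reported use of cannabis on at least 10 out of the past 30 days or submit a positive qualitative urinary cannabinoid test at screening".

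**Outcome (sections 3.0 and 9.0).** The primary endpoint, 7-day point prevalence abstinence at Week 12, "will be assessed via biochemical verification and participant self-report". On the biochemical side, "Urinary cotinine (a metabolite of nicotine) will be the primary indicator of tobacco abstinence", and "Abstinence criteria for quantitative cotinine will be set at 80 ng/ml". The instant-read cotinine strip serves contingency management: "Compensation will be delivered contingent on tobacco abstinence at weekly visits starting at Week 2", at $20 per visit and at most $220.

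**Schedule (Table 2).** The row "Urine Cotinine (lab assay and instant-read" is marked at every visit, screening included. No eligibility criterion uses the lab value, and section 10.0 describes no exclusion or sensitivity analysis based on it.

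**The concern.** Entry and outcome can rest on different markers. Someone admitted on CO alone has not been shown to be above the cotinine level that later separates smokers from quitters. If that person started below 80 ng/ml, a Week 12 value below 80 ng/ml says nothing about quitting. Self-report would not catch the case either: a person who overstated smoking at entry can truthfully report none at Week 12. Such a participant could also receive abstinence payments without having changed behaviour.

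This matters more here than in an ordinary cessation trial because cannabis use is the exposure under study. CO is a general product of combustion, so it may be a weaker sign of cigarette smoking in people who smoke cannabis. If so, false successes would collect mainly among co-users and shrink the difference that Hypothesis 1 predicts. The background section says that a finding of no impact may make it unnecessary to encourage cannabis cessation in unmotivated co-users, so an error toward no difference would have practical consequences.

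**Working it through.** **Is the route open?** Set the rules side by side:

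- Criterion d is met by CO of 7 ppm or more, whatever the cotinine result.
- Criterion c requires daily smoking, but the only biochemical check on it is criterion d.
- Abstinence is verified at 80 ng/ml of urinary cotinine, together with self-report.
- Nothing links screening cotinine to 80 ng/ml.

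So a participant can enrol below the abstinence cut-off, provided that the reported smoking is overstated or very light.

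**Inputs for the size.** From section 10.0: abstinence 45% in tobacco-only users and 20% in co-users, 2:1 allocation, 80% power, 5% type 1 error, base sample 82 and 41. Two-sided testing is assumed because sidedness is not stated. The share x of co-users entering below 80 ng/ml is not in the documents; 0% to 10% is shown.

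**The plan's own figure.** With unpooled variance, the smaller group needs

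n = (1.96 + 0.842)² × (0.45 × 0.55 + 0.20 × 0.80 / 2) / 0.25² = 41.1,

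which agrees with 41 and 82.

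**Worst case.** Every such entrant counts as abstinent and the rest quit at 20%:

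apparent co-user rate p = 0.20(1 − x) + x = 0.20 + 0.80x

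power = Φ[(0.45 − p) / √(0.45 × 0.55/41 + p(1 − p)/82) − 1.96]

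| x | p | Gap (points) | Power |
|---|---|---|---|
| 0% | 20.0% | 25.0 | 0.799 |
| 2% | 21.6% | 23.4 | 0.739 |
| 5% | 24.0% | 21.0 | 0.637 |
| 10% | 28.0% | 17.0 | 0.454 |

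For x = 2%: √(0.2475/41 + 0.1693/82) = 0.0900; 0.234/0.0900 − 1.96 = 0.64; Φ(0.64) = 0.74.

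In the 139 co-users of section 10.0, 2% is about 3 people (0.02 × 139 = 2.8) and 5% is about 7 (0.05 × 139 = 6.95).

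**Full sample.** Scaling 139/69 by 0.75 × 0.75, for the plan's R² and attrition allowances, leaves 78.2 and 38.8. The pooled-variance formula then gives 0.798, 0.737, 0.634 and 0.450 for the same four shares, so the picture does not change.

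**Same share in both cohorts.** The tobacco-only rate becomes 0.45 + 0.55x. On the same scaled sample, 5% gives 47.75% versus 24.0% and power 0.733; 10% gives 50.5% versus 28.0% and power 0.667. A non-differential problem costs less, but still costs something.

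**The case against.** The case against giving this much weight is strong on several points.

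- **Entry is not CO alone, and the endpoint is not cotinine alone.** A reader might infer that any cannabis smoker could walk in on CO and be scored a quitter on cotinine. Criterion c and the self-report component rule that out as a general claim; it takes overstated or very light smoking at entry. This stands.
- **One-sided error.** A reader might infer that the error falls on co-users only. The documents nowhere say that cannabis smoke raises breath CO, and criterion d applies equally to both cohorts. Section 2.0 also describes blunts made with cigar wrappers; tobacco from these could keep co-user cotinine positive and close the route for them. This stands: the direction is plausible, not established.
- **Strip versus lab value.** A negative strip cannot be read as below 80 ng/ml, because the strip's cut-off is not given. This stands, and it shapes the fix.
- **Other safeguards.** There are a phone screen, interviews, a 30-day timeline follow-back, the FTND, lead-in diaries, chart checks for patients of the institution, and an exclusion for concerns that could confound interpretation. These reduce the risk. Most are self-report, however, and none obliges staff to act on a low screening cotinine.
- **Incentives.** The $1,050 maximum is open to both cohorts, abstinence payments are at most $220 of it, and a participant must accept 12 weeks of varenicline with twice-daily dosing videos. Nothing suggests that payment draws in more co-users.
- **The size is assumed.** The share x has no source, and the worst case ignores the plan's 25% attrition among such entrants. This stands; the table is an illustration, not an estimate.

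**Conclusion.** The point holds in a limited form. The biochemical part of entry can be met without cotinine, abstinence is verified mainly by cotinine, and no rule or analysis closes the gap although the data are scheduled. Someone with overstated or very light smoking can enrol already below the abstinence marker and count as a quitter.

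The documents do not show how often this would happen, or that it would happen more among co-users. The share is probably small. If 2% of co-users entered this way and all counted as abstinent, power would fall from about 80% to about 74%; at 5%, to about 64%. Those figures rest on the assumed share, on every such entrant being scored abstinent, and on none entering the tobacco-only cohort this way. This is a minor issue, and a cheap improvement to the plan.

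**What to change.** 1. In criterion d, require a positive cotinine test at screening in both cohorts and keep breath CO as a descriptive measure.
2. Because the strip's cut-off is not stated, a positive strip does not guarantee a value above 80 ng/ml. Pre-specify a report of screening lab cotinine by cohort, including the number below 80 ng/ml. This would measure the unknown share directly.
3. Pre-specify a sensitivity analysis of Aim 1 that excludes participants whose screening lab cotinine is below 80 ng/ml. The exclusion uses a value taken before treatment, so it does not condition on response.

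Items 2 and 3 also cover anyone already enrolled on CO alone.

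Cost: a one-line amendment to eligibility and a short addition to section 10.0. Strip and lab cotinine are already scheduled at screening, and the planned contrast and sample size do not change. The downside is that an occasional genuine light smoker with a negative strip is not enrolled.

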5.0 Number of Subjects

A total of 270 participants will be consented with the goal of attaining a total final sample size of 208 (137 co-users, 71 tobacco only users) participants.

6.0 Setting

The research will be conducted at three study sites; 1) the offices of the Addiction Sciences Division at the Medical University of South Carolina, located in the Roper Medical Office Building, 2) Behavioral Health Services (BHS) of Pickens County, located in Pickens, South Carolina, and 3) MUSC Florence. All locations have conducted research studies before and are equipped with several private interview rooms to conduct informed consent and participant visits, a room for conducting physicals and medical histories, bathrooms for collecting urine samples, and storage space for files and study supplies. When possible, remote procedures will be utilized as needed. Participants may engage with study staff at any of the participating sites to complete study procedures. Charleston and Pickens staff will conduct the majority of study procedures with Florence participants.

7.0 Recruitment Methods

This proposed study will enroll 208 participants over the course of 46 months, at a rate of 4.5 participants per month at both participating sites. Several tobacco trials at the Medical University of South Carolina (MUSC) have recruited adolescent and adult cigarette smokers at a rate of 3-5 participants per month (NIDA grants U01DA031779; P50DA16511; R34 DA042228). BHS has experience with recruiting substance using populations into research studies, and similar methods of recruitment will be used in Pickens (and surrounding areas) as are being used in the Charleston area. A recruitment goal of 4.5 enrolled participants per month at both study sites is a reasonable target for the current study.

Our research team has used a number of successful recruitment methods to reach and enroll cigarette smokers and cannabis users. We will implement similar recruitment strategies. Since this study is focused on tobacco treatment, we will employ advertisements that focus on tobacco treatment-seekers, but also will advertise to those using both tobacco and cannabis, especially later in the study when only tobacco-cannabis co-users are needed for enrollment. Several tobacco studies conducted by our research team (in Charleston) fall under the umbrella of “Project Quit,” which has general advertisements targeting smokers of all ages and motivation levels. Through marketing of the “Project Quit” brand and continued activity, such as social media educational posts or presence at community events, we maintain a constant presence in the Charleston and surrounding areas, rather than having specific recruitment for one study at a time. This has been a successful recruitment campaign for several research studies. Each study is unique, with its own exclusion criteria, and competition between studies for participants has been minimal. All cigarette smokers interested in research opportunities call or text the same phone number and trained research staff are able to triage interested participants based on their characteristics and interest in quitting. Successful methods of recruitment that have been used previously will be used for this study and include (but are not limited to): print and internet-based recruiting methods (i.e. newspaper advertisements, flyers, billboards, buses, advertisements on Facebook, or other social media platforms, posting on Craigslist, etc.), tv or radio commercials (including streaming services, etc.), primary care, urgent care, and/or hospital or physician referrals (MUSC affiliated clinics or independent medical facilities), postings at local colleges with proper approval(s) (i.e. College of Charleston, The Citadel, Trident Technical Institute, Clemson University, etc.), etc. Potential participants will be directed to a REDCap survey where they can provide us with their contact information. The link to the contact card will be included in our materials such as our website and social media pages. We will also utilize TrialFacts and/or BuildClinical to aid in recruitment for this study (in addition to other potential clinical research organizations that may provide services during the course of

enrollment). TrialFacts, BuildClinical, and other clinical research advertising businesses utilize targeted digital media advertising to recruit participants.

We will also employ additional recruitment methods to research potential study participants. First, we will use ResearchMatch.org to contact potential study volunteers (using IRB approved language) to see if they may be interested and a good fit for this study. We will attempt to search for potential participants near study sites. Second, given the success of cold-contact recruitment used in a current study (Pro105269) and at MUSC generally to reach a wide range of patients that might not otherwise take part in research studies, we propose to use cold contact methods to reach smokers in study location areas. Patient reports will be requested from the MUSC Biomedical Informatics Center [BMIC]). We will ask for searches of the medical record that identify smokers, ages 18-40, within 30-40 miles of Charleston, Pickens, or Florence from MUSC and all regional hospitals. BMIC will gather contact and demographic information (name, phone number, street address, zip code, etc.) for potential study participants, as well as smoking status. All potentially eligible patients will be selected for recruitment unless they have specifically opted out of research communication. Patients' opt-out preferences will be documented in their REDCap Research Contact Form. The study team will not cold contact any patients who already have opt-out preferences noted in their electronic health records.

Additionally, Respondent-Driven Sampling (RDS) will be used to enhance recruitment. The RDS sampling methodology is based on recruiting the eligible friends and acquaintances of each participant so that the sample "snowballs." Each eligible participant who is enrolled into the study, and agrees to take part in this recruitment assistance, is eligible to receive compensation for successful referrals. A referral will be instructed to call the study team to be screened for eligibility. If that person successfully enrolls into the study (i.e., completes the Day 0 visit and begins taking study medication), the participant who referred them can receive \$30 in compensation for each eligible participant that is referred and enrolled in the study. The research team has used these methods successfully in the past.

Interested participants will have a brief phone screen conducted to ensure that participants are the appropriate age and are regular tobacco users. Eligible participants will be scheduled for a screening visit. Participants will complete an in-lab screening visit with trained study staff.

